### **3.4.5      Rationale for Optional Active Treatment Extension**

The optional ATE period will explore the durability of clinical response and remission and the long-term safety of vixarelimab over an extended treatment period of [REDACTED]. The design of the optional ATE period will allow all eligible patients who have completed the induction period to be treated with vixarelimab, regardless of initial treatment assignment.

## **4.            MATERIALS AND METHODS**

### **4.1            PATIENTS**

Approximately 210 patients with moderate to severe UC will be enrolled in this study.

#### **4.1.1            Inclusion Criteria**

##### **4.1.1.1            General Inclusion Criteria for All Patients**

All patients must meet the following criteria for study entry, as well as additional criteria for advanced failures (Section 4.1.1.2) or conventional failures (Section 4.1.1.3):

- Signed Informed Consent Form
- Adults ( $\geq 18$  years of age or per local standards) at time of signing Informed Consent Form
- Ability to comply with the study protocol
- Diagnosis of UC established at least 3 months prior to screening, confirmed by clinical and endoscopic evidence during screening

The diagnosis of UC should be corroborated by histopathology and documented by a histopathology report. A histopathologic examination should be performed at screening if no prior report is readily available.

- [REDACTED]
- [REDACTED]
- Any permitted background UC therapy must be at stable doses, as outlined below:
  - May be receiving oral 5-ASA compounds at a dose that has been stable for  $\geq 2$  weeks immediately prior to screening *endoscopy*.
  - May be receiving oral corticosteroid therapy at a dose of  $\leq 20$  mg/day of prednisone (or equivalent) that has been stable for  $\geq 2$  weeks immediately prior to screening *endoscopy*.
  - May be receiving oral probiotic (e.g., Culturelle, *Saccharomyces boulardii*), at a dose has been stable for  $\geq 2$  weeks immediately prior to screening *endoscopy*.
  - May be receiving AZA, 6-MP, or MTX at a dose that has been stable for  $\geq 12$  weeks immediately prior to screening *endoscopy*.
- Must have received a colonoscopy within 2 years prior to screening or be willing to undergo a colonoscopy in lieu of a flexible sigmoidoscopy at screening. This colonoscopy must:
  - Confirm disease extent, defined as 1) left-sided colitis (inflammation up to the splenic flexure), 2) extensive colitis (inflammation beyond the splenic flexure but not involving the entire colon), or 3) pancolitis (inflammation of the entire colon)
  - Include removal of any adenomatous polyps
  - Include surveillance to detect dysplasia per local standard of care for all patients with left-sided colitis of  $> 12$  years' duration or extensive colitis or pancolitis of  $> 8$  years' duration
- For women of childbearing potential: agreement to remain abstinent (refrain from heterosexual intercourse) or use contraception, *and agreement to refrain from donating eggs*, as defined below:

Women must remain abstinent or use two methods of contraception, including at least one method with a failure rate of  $< 1\%$  per year, during the treatment period and for [REDACTED] after the final dose of study treatment. *Women must refrain from donating eggs during this same period.*

A woman is considered to be of childbearing potential if she is postmenarchal, has not reached a postmenopausal state ( $\geq 12$  continuous months of amenorrhea with no identified cause other than menopause), and is not permanently infertile due to surgery (i.e., removal of ovaries, fallopian tubes, and/or uterus) or another cause as determined by the investigator

(e.g., Müllerian agenesis). Per this definition, a woman with a tubal ligation is considered to be of childbearing potential. The definition of childbearing potential may be adapted for alignment with local guidelines or regulations.

Examples of contraceptive methods with a failure rate of < 1% per year include bilateral tubal ligation, male sterilization, hormonal contraceptives that inhibit ovulation, hormone-releasing intrauterine devices, and copper intrauterine devices.

A barrier method may be used as the second contraceptive method.

The reliability of sexual abstinence should be evaluated in relation to the duration of the clinical trial and the preferred and usual lifestyle of the patient. Periodic abstinence (e.g., calendar, ovulation, symptothermal, or postovulation methods) and withdrawal are not adequate methods of contraception. If required per local guidelines or regulations, locally recognized adequate methods of contraception and information about the reliability of abstinence will be described in the local Informed Consent Form.

- For men: agreement to remain abstinent (refrain from heterosexual intercourse) or use a condom, and agreement to refrain from donating sperm, as defined below:

With a female partner of childbearing potential or pregnant female partner, men must remain abstinent or use a condom during the treatment period and for [REDACTED] after the final dose of study treatment to avoid exposing the embryo. Men must refrain from donating sperm during this same period.

The reliability of sexual abstinence should be evaluated in relation to the duration of the clinical trial and the preferred and usual lifestyle of the patient. Periodic abstinence (e.g., calendar, ovulation, symptothermal, or postovulation methods) and withdrawal are not adequate methods of preventing drug exposure. If required per local guidelines or regulations, information about the reliability of abstinence will be described in the local Informed Consent Form.

#### **4.1.1.2 Inclusion Criteria for Advanced Failures**

Advanced failure patients must meet the following criteria for study entry:

- Inadequate response, loss of response to, or intolerance to [REDACTED] of approved advanced therapies, which include biologics and targeted small molecules, as defined by the following:
  - Inadequate response is defined by persistent signs and symptoms of active disease despite at least one induction regimen of advanced therapy.
  - Loss of response is defined by the recurrence of symptoms during maintenance dosing of advanced therapy following prior clinical benefit (discontinuation despite clinical benefit or discontinuation due to loss of access does not qualify).
  - Intolerance is defined by history of adverse effect necessitating treatment discontinuation of advanced therapy (including, but not limited to infusion-related reaction, demyelination, congestive heart failure, infection).

#### 4.1.1.3 Inclusion Criteria for Conventional Failures

Conventional failure patients must meet the following criteria for study entry:

- Inadequate response, loss of response to, or intolerance to prior conventional UC therapies (immunosuppressant and/or corticosteroid treatment)

Failure to only 5-ASA treatment is not sufficient.

Inadequate response to, loss of response to, or intolerance to prior immunosuppressant treatment (i.e., AZA, 6-MP, or MTX), is defined as one or more of the following:

- Persistent signs and symptoms of active disease despite treatment with at least one 12-week regimen of AZA ( $\geq 1.5$  mg/kg/day) or 6-MP ( $\geq 0.75$  mg/kg/day) and/or MTX  $\geq 15$  mg/week)
- Persistent signs and symptoms of active disease despite a 6-thioguanine nucleotide level of  $\geq 230$  pmol/ $8 \times 10^8$  RBCs (as measured by quantitative high-performance liquid chromatography or liquid chromatography/tandem mass spectrometry) during at least one 12-week regimen of oral AZA or 6-MP at a stable or increasing dose
- History of intolerance to, *or inability to titrate doses to levels listed above for*, AZA, 6-MP, or MTX *because of the risk of adverse effects* (including, but not limited to, nausea/vomiting, abdominal pain, pancreatitis, liver function test abnormalities, lymphopenia, TPMT genetic mutation, or infection)

Inadequate response, loss of response, or intolerance to corticosteroid treatment is defined as one or more of the following:

- Steroid refractory: persistent symptoms of active disease despite treatment with at least one 4-week induction regimen that included  $\geq 30$  mg/day of oral prednisone (or equivalent) for at least 2 weeks or  $\geq 30$  mg/day of IV prednisone (or equivalent) for at least 1 week
  - Steroid dependent: *one failed attempt to taper corticosteroids below a dose equivalent to 10 mg/day of oral prednisone (or equivalent) within 3 months, or disease relapse within 3 months after corticosteroid discontinuation*
  - Steroid intolerant: history of intolerance to corticosteroids (including, but not limited to, Cushing's syndrome, osteopenia/osteoporosis, hyperglycemia, insomnia, or infection)
- Conventional failures who have received a prior advanced therapy but do not meet inclusion criteria for advanced failures (Section 4.1.1.2) may be enrolled, in consultation with the Medical Monitor

Patients must have discontinued the biologic for reasons other than inadequate response, loss of response, or intolerance (e.g., change of insurance, well controlled disease), and must meet the criteria for inadequate response, loss of response, or intolerance to immunosuppressants and/or corticosteroids defined above.

#### 4.1.2 **Exclusion Criteria**

Patients who meet any of the following criteria will be excluded from study entry:

- Pregnancy or breastfeeding or intention to become pregnant during the study or within [REDACTED] after the final dose of study treatment  
Women of childbearing potential must have a negative serum pregnancy test result at screening and a negative urine pregnancy test on Day 1 prior to initiation of study treatment.
- History of alcohol, drug, or chemical abuse  $\leq 2$  years prior to screening
- Prior extensive colonic resection, subtotal or total colectomy, or planned surgery for UC
- Past or present ileostomy or colostomy
- Diagnosis of Crohn's disease or indeterminate colitis
- Suspicion of ischemic colitis, radiation colitis, or microscopic colitis
- Diagnosis of toxic megacolon within 12 months of initial screening visit
- Past or present fistula or abdominal abscess
- History or current evidence of unresected adenomatous colonic polyps or colonic mucosal dysplasia
- Any stricture (stenosis) of the colon that precludes endoscopic evaluation
- Diagnosis or suspicion of primary sclerosing cholangitis
- History of *known or suspected* allergic reaction or anaphylactic reaction to a biologic agent, *including vixarelimab or its excipients*
- Previous treatment with vixarelimab or current participation in Study GB44496
- *Inadequate response or loss of response to* previous treatment *of UC* with tofacitinib, upadacitinib, or other systemic JAK inhibitor
- Treatment of UC with approved biologic agents within 8 weeks or 5 half-lives prior to screening *endoscopy*, whichever is longer

If there is proper documentation of undetectable drug level measured by a commercially available assay for any of the approved biologics, there is no minimum washout prior to screening *endoscopy*.

- Treatment of UC with approved non-biologic therapies other than those specifically listed as permitted medications (Section 4.4) within 2 weeks or 5 half-lives prior to screening *endoscopy*, whichever is longer
- Use of IV corticosteroids within 2 weeks prior to screening *endoscopy*
- Treatment with corticosteroid enemas or suppositories and/or topical (rectal) 5-ASA preparations within 2 weeks prior to screening *endoscopy*
- Apheresis (e.g., Adacolumn® apheresis) within 2 weeks prior to screening *endoscopy* or intent to receive during the study
- Chronic nonsteroidal anti-inflammatory drug (NSAID) use

Occasional use of NSAIDs [e.g., headache, arthritis, myalgias, or menstrual cramps] and aspirin (up to 325 mg/day) is permitted.

- Participation in an investigational study involving non-biologic therapy within *4 weeks* or 5 half-lives of the investigational product (whichever is greater) prior to screening, or biologic therapy (including vaccines) within 8 weeks or 5 half-lives of the investigational product (whichever is greater) prior to screening
- Treatment with any live-attenuated vaccine within 4 weeks prior to screening or intended to receive such during the study.

Uses of non-live (inactivated) vaccines are allowed.

- Treatment with immunoglobulin or blood products within 4 weeks prior to screening, or any condition that is likely to require such treatment during the course of the study, unless the treatment is deemed acceptable by the investigator, in consultation with the Medical Monitor
- Conditions other than UC that could require treatment with > 20 mg/day of prednisone (or equivalent) during the course of the study, *per the investigator's assessment*
- Significant uncontrolled medical condition or comorbidity, such as cardiac (e.g., moderate to severe heart failure New York Heart Association Class III/IV or historical evidence of left ventricular ejection fraction <35%), pulmonary, renal, hepatic, endocrine, or gastrointestinal disorders (excluding UC) that in the opinion of the investigator, would confound the study results or compromise patient safety
- Hospitalized (other than for elective reasons) during the screening period
- History of malignancy within the 5 years prior to screening, with the exception of basal cell or squamous cell skin neoplasms

In addition, a malignant diagnosis or condition that occurred more than 5 years prior to screening, and any basal cell or squamous cell neoplasm must be considered cured, inactive, and not under treatment.

- History or presence of complete left bundle branch block, second- or third-degree atrioventricular heart block, *or other abnormal ECG finding during screening that is deemed clinically significant by the investigator*
- QT interval corrected through use of Fridericia's formula (QTcF) >450 ms if patient is male or QTcF >470 if patient is female

For male or female patients with QRS > 120: QTcF >480 ms

- Acquired or congenital immunodeficiency
- Positive HIV antibody test at screening
- Positive hepatitis C virus (HCV) antibody test result accompanied by a positive HCV RNA test at screening
- Positive test results for hepatitis B infection at screening, defined as meeting either of the following criteria:
  - Positive hepatitis B surface antigen (HBsAg) test at screening

- Quantitative HBV DNA  $\geq 20$  IU/mL in patients with a negative hepatitis B surface antibody (HBsAb) test and positive total hepatitis B core antibody (HBcAb) test
- Positive for tuberculosis (TB) during screening or within 3 months prior to screening, defined as a positive *interferon- $\gamma$  release assay (IGRA; e.g., QuantiFERON®-TB Gold or T-SPOT.TB)*, or if not available, a positive purified protein derivative (PPD) skin test according to Centers for Disease Control and Prevention guidelines, with the following exceptions:
  - Patients with a history of Bacillus Calmette-Guérin (BCG) vaccination who have a positive PPD skin test will not be excluded if they have a negative IGRA at screening
  - Patients who have a positive or indeterminate IGRA and patients with no history of BCG vaccination who have a positive PPD skin test will not be excluded if they meet all of the following criteria:
    - No symptoms consistent with TB
    - Documented history of a completed course of adequate prophylaxis (completed treatment for latent TB) per local standard of care prior to screening, *or initiation of treatment for latent TB per local standard of care at least 3 weeks prior to randomization with intention to complete treatment while on study*
    - For patients not currently on latent TB treatment, no known exposure to a case of active TB after most recent completed prophylaxis, if applicable*
    - No evidence of active TB on chest X-ray performed during screening or within 3 months prior to screening
- Evidence of *C. difficile* (as assessed by *C. difficile* toxin testing) or other intestinal pathogens (as assessed by stool culture and ova and parasite evaluation) at screening or within 30 days prior to screening
- Colonic biopsy positive for CMV, as determined by histologic examination or immunohistochemistry per local standards, at screening or within 30 days prior to screening
  - Laboratory confirmation of CMV from a colon biopsy sample is required during screening evaluation only if clinical suspicion is high and to determine the need for CMV treatment.*
- Clinically significant abnormality on laboratory tests during screening (hematology, serum chemistry, and urinalysis) that, in the opinion of the investigator, may pose an additional risk in administering study treatment to the patient
- ALT, AST, or ALP  $> 2.5 \times$  upper limit of normal (ULN), total bilirubin  $> 2 \times$  ULN, or presence of abnormalities in synthetic liver function tests judged to be clinically significant by the investigator
  - Patients with known Gilbert syndrome who have unconjugated hyperbilirubinemia will not be excluded.

- ANC  $< 1.5 \times 10^9/L$  (1500/ $\mu L$ ), with one exception:

Patients with benign ethnic neutropenia (BEN): ANC  $< 1.3 \times 10^9/L$  (1300/ $\mu L$ )

BEN (also known as constitutional neutropenia) is an inherited cause of mild or moderate neutropenia that is not associated with any increased risk for infections or other clinical manifestations (Atallah-Yunes et al. 2019). BEN is referred to as ethnic neutropenia because of its increased prevalence in people of African descent and other specific ethnic groups.

- Absolute lymphocyte count  $< 0.5 \times 10^9/L$  (500/ $\mu L$ )

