##### ***Samples for Central Laboratory Tests***

Samples for the following laboratory tests will be sent to one or several central laboratories for analysis:

- Urine drug screening
- Hematology: WBC count, RBC count, hemoglobin, hematocrit, platelet count, and differential count (neutrophils, eosinophils, basophils, monocytes, lymphocytes, other cells)
- Chemistry panel (serum or plasma): bicarbonate or total carbon dioxide (if considered standard of care for the region), sodium, potassium, chloride, glucose, BUN or urea, creatinine, total protein, albumin, phosphate, calcium, total and direct bilirubin, ALP, ALT, AST, urate, and lactate dehydrogenase

- Coagulation: INR, aPTT, and PT
- HIV serology: HIV-1/2 antibody
- HBV serology: HBsAg, HBsAb, and total HBcAb for all patients
 

If a patient has a negative HBsAg and HBsAb tests and a positive total HBcAb test at screening, an HBV DNA test must also be performed to determine if the patient has an HBV infection.
- HCV serology: HCV antibody for all patients
 

If a patient has a positive HCV antibody test at screening, an HCV RNA test must also be performed to determine if the patient has an HCV infection.
- TB test: *IGRA* or, if *IGRA* is unavailable, PPD skin test
 

Test may be performed locally.
- Serum pregnancy test
 

All women of childbearing potential (defined in Section 4.1.1) will have a serum pregnancy test performed at screening. Urine pregnancy tests will be performed at specified subsequent visits at the site's local laboratory. If a urine pregnancy test is positive, it must be confirmed by a serum pregnancy test.

Test for follicle-stimulating hormone may be performed at screening to confirm postmenopausal state, if required per local guidelines.
- Serum CRP
- Fecal calprotectin

The following PK and biomarker samples will be sent to the Sponsor or a designee for analysis:

- Serum samples for PK analysis
- Serum samples for immunogenicity analysis
- Serum samples for exploratory biomarker research and PK/PD analyses
- Stool samples for exploratory biomarker research that may include, but will not be limited to, microbiota analyses and inflammatory proteins

*Note: These samples will not be collected or analyzed in China (see Appendix 9).*

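### The TB exclusion is triggered only by a positive test, so its four safety conditions do not, as written, bind a patient whose only TB result is an indeterminate IGRA

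*Combined protocol and SAP*

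**What the plan says.** Section 4.1.2 is a list of exclusions, and a patient is kept out by meeting an item on it: "Patients who meet any of the following criteria will be excluded from study entry".

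The TB item opens with "Positive for tuberculosis (TB) during screening or within 3 months prior to screening, defined as a positive" IGRA, and continues "or if not available, a positive purified protein derivative (PPD) skin test". Two exceptions follow.

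- The first concerns BCG-vaccinated patients with a positive PPD. They are released if their screening IGRA is negative.
- The second concerns "Patients who have a positive or indeterminate IGRA and patients with no history of BCG vaccination who have a positive PPD skin test". These patients "will not be excluded if they meet all of the following criteria". There are four: absence of TB symptoms; latent TB treatment completed before screening or begun at least 3 weeks before randomization; for those not on treatment, no known contact with active TB since completing prophylaxis; and "No evidence of active TB on chest X-ray performed during screening or within 3 months prior to screening".

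Section 4.5.8 names the TB test as an IGRA or, if that "is unavailable, PPD skin test". It gives no instruction for an indeterminate result.

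**The concern.** An exception can only relieve patients whom the rule has already caught. Here the rule catches positive tests, while the exception sets terms for positive and indeterminate tests. For the indeterminate group the terms hang on nothing: the patient is not excluded to begin with, so meeting or failing the terms changes nothing.

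What is at stake is TB safety at entry. Section 4.1.1.1 allows patients to enter on oral corticosteroids of up to 20 mg/day prednisone, or on AZA, 6-MP or MTX, so TB screening matters in this population. In the visible text, TB symptoms and an X-ray finding of active TB enter eligibility by name only through this second exception. The wording also decides what counts as a deviation. Section 9.2 does not allow eligibility waivers, so enrolling an indeterminate patient who fails a condition is compliant on the literal reading and a deviation on the intended one. Sites and monitors could classify the same case differently.

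**Working it through.** No arithmetic applies, and the plan gives no figure to reproduce. The criterion can be checked as a logical rule.

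**Inputs, all from Section 4.1.2**

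- Trigger T: a positive IGRA during screening or in the previous 3 months, or a positive PPD where PPD counts.
- Exception E1: BCG history, positive PPD and a negative screening IGRA.
- Exception E2: a positive IGRA, an indeterminate IGRA, or a positive PPD without BCG history, together with all four conditions C1 to C4.
- Rule: excluded = T and not (E1 or E2).

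**Applying the rule as written**

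1. Positive IGRA. T is true. The patient is excluded unless C1 to C4 all hold, so the conditions bind.
2. IGRA not available, positive PPD, no BCG history. T is true and the conditions bind.
3. Indeterminate screening IGRA, but a positive IGRA in the previous 3 months. T is true through the earlier result and the conditions bind.
4. Indeterminate IGRA and a positive PPD, where the PPD is allowed to count. T is true. E1 cannot apply because the IGRA is not negative, so only E2 can release the patient and the conditions bind.
5. Indeterminate IGRA as the only TB result of note. T is false. The patient is not excluded whether 0, 1, 2, 3 or 4 of the conditions hold. None binds.

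**Applying the rule with the trigger widened to a positive or indeterminate IGRA**

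Cases 1 to 4 come out as before. In case 5, T becomes true and the patient is excluded unless all four conditions hold, which is what E2 presupposes.

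**Is case 5 covered elsewhere?**

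- The general laboratory exclusion in Section 4.1.2 is limited to hematology, serum chemistry and urinalysis. IGRA is outside it.
- The exclusion for serious uncontrolled illness, which includes pulmonary disease, turns on whether the condition "in the opinion of the investigator, would confound the study results or compromise patient safety". That is a judgment, not a TB rule.
- Section 3.1.1 treats the chest X-ray as a screening assessment but attaches no eligibility consequence to it.
- Section 4.5.1 requires all screening evaluations to be reviewed before enrollment, but against the criteria as they stand.
- Section 4.5 (clinical assessment before each dose) and Section 4.6.1 (discontinuation to be considered for active or reactivated TB) operate after entry.

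None of these says how an indeterminate IGRA is to be handled.

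**The case against.** The strongest reply is that trigger and exceptions form one criterion and should be read together. Telling a site that indeterminate patients escape exclusion on four conditions tells it that they are otherwise excluded; any other reading makes the word *indeterminate* redundant. That is a fair account of the intent, and most sites would probably act on it. It also confirms that the definition and its exception do not match.

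A second reply is that the gap is narrow, and this stands. A reader might infer that a patient with an indeterminate IGRA can never be excluded under the TB criterion. The documents do not support that: a positive IGRA in the look-back period triggers the exclusion, as does a positive PPD where it counts. How far the PPD route reaches is arguable. The trigger and Section 4.5.8 confine PPD to cases without an IGRA, yet the first exception weighs a positive PPD against an IGRA result, which suggests that both may be in play. Even on the generous view, a PPD-negative or untested patient stays uncovered.

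A reader might also infer that the plan lets in patients with active TB unchecked. It does not. Imaging is part of screening, the investigator can exclude on safety grounds, and pre-dose assessment and discontinuation provisions follow. The more realistic lapse is an asymptomatic patient with an indeterminate result who enters without latent TB treatment.

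**Conclusion.** The concern holds in a limited form. For a patient whose only TB result is an indeterminate IGRA, with no positive IGRA in the previous 3 months and no qualifying positive PPD, the exclusion as written is not met and all four conditions fall away, contrary to the evident intent.

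This is a minor wording error in an operative safety criterion. It does not touch sample size, significance level, endpoints or analysis. Its frequency cannot be stated, because the documents give no rate of indeterminate results and no indication of how many such patients would fail a condition. The conclusion rests on a literal reading of the visible text and on the absence there of any other rule for an indeterminate IGRA. Confidence is high that the text is mismatched; nothing is claimed about how often it would matter.

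**What to change.** In the definition of the TB exclusion in Section 4.1.2, change *a positive* IGRA to *a positive or indeterminate* IGRA. The four conditions then bind every patient the second exception names, and no other part of the criterion needs to change.

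The cost is two words, with no consequence for design or analysis. The downside is that a few patients with an indeterminate result may be delayed or not enrolled. Because the definition looks back 3 months, the sponsor may wish to state whether a repeat IGRA can replace an indeterminate one. That would be a new clinical rule for the sponsor to decide; the documents do not call for it and the correction does not depend on it.
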